### 7.2.3 CLASSIFICATION OF AN ADVERSE EVENT

#### 7.2.3.1 SEVERITY OF EVENT

For adverse events (AEs), the following guidelines will be used to describe severity:

- **Mild** – Events require minimal or no treatment and do not interfere with the participant's daily activities.
- **Moderate** – Events result in a low level of inconvenience or concern with the therapeutic measures. Moderate events may cause some interference with functioning.
- **Severe** – Events interrupt a participant's usual daily activity and may require systemic drug therapy or other treatment. Severe events are usually potentially life-threatening or incapacitating. Of note, the term "severe" does not necessarily equate to "serious."

---

#### 7.2.3.2 RELATIONSHIP TO STUDY INTERVENTION

All adverse events (AEs) must have their relationship to study intervention assessed by the researchers who examine and evaluate the participant based on temporal relationship and his/her clinical judgment. The degree of certainty about causality will be graded using the categories below. In a clinical trial, the study product must always be suspect.

- **Related** – The AE is known to occur with the study intervention, there is a reasonable possibility that the study intervention caused the AE, or there is a temporal relationship between the study intervention and event. Reasonable possibility means that there is evidence to suggest a causal relationship between the study intervention and the AE.
- **Not Related** – There is not a reasonable possibility that the administration of the study intervention caused the event, there is no temporal relationship between the study intervention and event onset, or an alternate etiology has been established.

---

#### 7.2.3.3 EXPECTEDNESS

The Principal Investigator will be responsible for determining whether an adverse event (AE) is expected or unexpected. An AE will be considered unexpected if the nature, severity, or frequency of the event is not consistent with the risk information previously described for the study intervention.

---

### 7.2.4 TIME PERIOD AND FREQUENCY FOR EVENT ASSESSMENT AND FOLLOW-UP

The occurrence of an adverse event (AE) or serious adverse event (SAE) may come to the attention of study personnel during study visits and interviews of a study participant presenting for medical care, or upon review by a study monitor.

All AEs including local and systemic reactions not meeting the criteria for SAEs will be captured on the appropriate case report form (CRF). Information to be collected includes event description, time of onset, clinician's assessment of severity, relationship to study product (assessed only by those with the training and authority to make a diagnosis), and time of resolution/stabilization of the event. All AEs occurring while on study will be documented appropriately regardless of relationship. All AEs will be followed to adequate resolution.

#### 7.2.5 ADVERSE AND SERIOUS ADVERSE EVENT REPORTING

All serious adverse events will be reported to the IRB according to regulatory requirements. The Principal Investigator will report to the sponsor any serious adverse event in a timely manner. All serious adverse events (SAEs) will be followed until satisfactory resolution.

### 7.3 UNANTICIPATED PROBLEMS

#### 7.3.1 DEFINITION OF UNANTICIPATED PROBLEMS (UP)

The Office for Human Research Protections (OHRP) considers unanticipated problems involving risks to participants or others to include, in general, any incident, experience, or outcome that meets all of the following criteria:

- Unexpected in terms of nature, severity, or frequency given (a) the research procedures that are described in the protocol-related documents, such as the Institutional Review Board (IRB)-approved research protocol and informed consent document; and (b) the characteristics of the participant population being studied;
- Related or possibly related to participation in the research (“possibly related” means there is a reasonable possibility that the incident, experience, or outcome may have been caused by the procedures involved in the research); and
- Suggests that the research places participants or others at a greater risk of harm (including physical, psychological, economic, or social harm) than was previously known or recognized.

#### 7.3.2 UNANTICIPATED PROBLEM REPORTING

The investigator will report unanticipated problems (UPs) to the reviewing Institutional Review Board (IRB). The UP report will include the following information:

- Protocol identifying information: protocol title and number, PI's name, and the IRB project number;
- A detailed description of the event, incident, experience, or outcome;
- An explanation of the basis for determining that the event, incident, experience, or outcome represents an UP;
- A description of any changes to the protocol or other corrective actions that have been taken or are proposed in response to the UP.

To satisfy the requirement for prompt reporting, UPs will be reported using the following timeline:

- UPs that are serious adverse events (SAEs) will be reported to the IRB within 10 working days of the investigator becoming aware of the event.
- Any other UP will be reported to the IRB within 10 working days of the investigator becoming aware of the problem.

## 8 STATISTICAL CONSIDERATIONS

### 8.1 STATISTICAL HYPOTHESES

- Primary Endpoint(s):

Unsafe crossings and start delays in virtual reality pedestrian crossings

- Secondary Efficacy Endpoint(s):

Other pedestrian safety outcomes, as assess in virtual and real world assessments

### 8.2 SAMPLE SIZE DETERMINATION

Sample size is driven by Specific Aims 1 and 3 in the grant submission. In our previous study comparing 4 pedestrian training groups including the laboratory VR (Schwebel, McClure, et al., 2014a), we observed after 6 training sessions an adjusted mean change from post to pre of 280 milliseconds in start delay (after accounting for baseline value; field and VR trials averaged). To conclude the smartphone group is not inferior to the laboratory VR group with 80% power and type I error rate of 0.05, assuming a common SD of 0.50 (similar to that observed previously) and a non-inferiority margin of 0.12 (reflecting reduction in the gap before initiating crossing from post to pre of no less than 160 milliseconds, 50% of the more ecologically-valid field trial reduction of 320 milliseconds seen previously in VR group, and also the more conservative estimate between field vs lab assessment; Schwebel, McClure, et al., 2014a; 50% recommended by Mulla et al., 2012), we require a sample size of 216 per group (total N = 432) based on a two-sample test of difference in means. To account for attrition, estimated conservatively from our previous study's 9% attrition rate, we will inflate the sample size by 15%, recruiting a total N of 498.

We expect the hypotheses tested in Specific Aim 3 will be sufficiently powered also. Specific Aim 3 has two primary outcomes. For start delay, we expect sufficient power as: (a) the SD of start delay should be smaller than that for Specific Aim 1 given the larger number of training trials, and (b) as the SD decreases, the sample size required to declare noninferiority with the same margin will be smaller. For unsafe crossings, in the previous VR study we observed a mean of 0.20 (SD=0.20) for the follow-up mean percent of unsafe crossings. We assume that after additional training sessions, the mean percent of unsafe crossings will decrease and the variation will also decrease. With 216 per group, and assuming conservatively that the standard deviation decreases from 0.20 to 0.18, with alpha=0.025 and a non-inferiority margin of 5%, we have 82% power. In reality, we anticipate that the standard deviation will decrease further yet, which will result in increases in power for this hypothesis (SD=0.17 → power=86%; SD=0.16 → power=90%).

### 8.3 STATISTICAL ANALYSES

Descriptive statistics for participants randomized to each intervention will be summarized for each outcome using standard measures of central tendency and variability. Several covariates may impact the relation between the intervention and the outcome measures of interest, including age, gender, temperament, attention during intervention, pedestrian experience, and verbal intelligence. Because children will be randomized to the interventions, we expect these covariates to be balanced across intervention groups. To test this, we will assess the relation between each covariate and intervention group. If differences emerge, those variables will be included as covariates in primary analyses. Primary inferential data analyses will address the study's three objectives. Specific Aim 1 is to test whether immersive training in the smartphone VR improves children's street-crossing skills after 6 training trials at a rate not inferior to improvement seen in the semi-immersive kiosk VR. Given its relevance especially during the early stages of learning pedestrian safety, start delay will serve as the primary dependent measure and the hypothesis of interest for testing change, assuming that an improvement is reflected by a negative value (that is, a lower post-training value is better), is:

$$H_0: \Delta_{LVR} - \Delta_{IVR} \geq \delta \text{ vs. } H_A: \Delta_{LVR} - \Delta_{IVR} < \delta$$

where  $\delta$  is the non-inferiority margin. We will perform ANCOVA to determine if the difference in change from post- to pre-intervention visits in the two groups falls below the non-inferiority margin, after adjustment for the baseline measure. If so, we will reject the null hypothesis and conclude training in the smartphone VR is not inferior to training in the kiosk VR. We will use similar methodology also to examine secondary outcome measures such as unsafe crossings and attention to traffic.

Specific Aim 2 is to (2a) demonstrate that most children achieve adult-level pedestrian functioning after 25 training sessions and (2b) demonstrate how many training sessions are sufficient to achieve this functioning. Because the safety of crossings is ultimately of greatest interest from a public health perspective, unsafe crossings will serve as the primary outcome for this aim; start delay will serve as a critical secondary outcome. Adult functioning will be estimated based on the performance of 311 healthy adults in four previous studies. Aim 2a will be evaluated via simple descriptive statistics to determine what percent of children achieve an unsafe crossings rate equivalent to adults in multiple simulated crossings. Aim 2b will also be evaluated descriptively, in this case by examining the average number of trials needed to achieve adult functioning across the sample, as well as the trajectory and distribution of that variable.

Specific Aim 3 is to test whether training in the smartphone VR improves children's street-crossing skills after 25 training trials, or fewer if adult functioning is achieved earlier, at a rate not inferior to improvement seen in the semi-immersive kiosk VR. Two dependent variables will be primary, start delay and unsafe crossings (other measures will be considered secondarily) and we will test the aim with the same hypothesis, analyses, and assumptions as in Specific Aim 1. Two sets of analyses will be conducted, one to test change from baseline to post-intervention and the second to test change from baseline to follow-up visits 6 months later.

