## 5 STUDY INTERVENTION

### 5.1 STUDY INTERVENTION(S) ADMINISTRATION

#### 5.1.1 STUDY INTERVENTION DESCRIPTION

##### Virtual Reality Platforms

Two virtual reality (VR) platforms will be used, the “kiosk” VR in a laboratory setting and the smartphone-based VR delivered via smartphone. In the kiosk system, children stand on a plywood curb and step down onto a pressure plate to trigger the system for crossing. The system runs on a single Windows 7 PC with an Intel Core i5-3330 3.0GHz Quad-Core desktop processor and GeForce GT 640 video card. The virtual environment is displayed on 3 vertically mounted Samsung MD55C 55” Direct-lit LED displays and is moved vertically on the displays to match the participant’s eye-level. In the smartphone system, children use a standard Android mobile smartphone inserted into a durable View-Master® VR viewer. The street-crossing simulator software on both systems are built on top of the Unity game engine with identical virtual environments, game play logic and data collection.

In both VR platforms, prior to children entering the VR, the researcher enters a walking speed (based either on the child's previously-measured walking speed in a separate location or age-based averages), gender, and skin tone (to select sex- and race-matched avatar). Children view a bi-directional roadway modeled after an actual street environment near a local school. Traffic density, traffic speed, and vehicle types are adjusted to researcher preferences and child skill level. Ambient and Doppler-accurate traffic noise are delivered. Over a dozen types of vehicles (including cars, SUVs, pick-ups, and also ambulances, school buses, etc.) appear in random order at researcher-determined frequencies. When children deem it safe, they step off the simulated curb to trigger a pressure plate (semi-immersion) or push a button (smartphone). In the kiosk VR, the virtual world view then changes from first to third-person, permitting children to view themselves crossing. This switch from first to third person happens seamlessly and most users do not even notice the switch when asked about it later. In the smartphone VR, the virtual world remains at first-person view, as the viewpoint follows the avatar across the street.

Following the avatar's crossing, the child is informed about the safety of crossing.

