### Training Protocol

Children will complete up to 25 training sessions. Training sessions will be scheduled about twice a week and will be identical in both groups except for the VR platform used. Children will engage in the VR for 3 sets of 15 crossings, or 45 crossings at each training session (expected duration ~30 minutes). The first two sets of crossings will be tailored to children's ability level, with traffic density set just beyond the level they previously succeeded crossing at. The third set of crossings will be standardized for all visits, at 30 MPH and 10 vehicles/minute/lane. Along with serving as a training trial, this third set will typically be a little easier for children, providing positive feedback and motivation for training. It also will offer a standardized assessment of ability.

All children will complete six visits to the laboratory for training. Following the sixth and all subsequent visits, we will monitor each child's number of unsafe crossings in the final standardized assessment.

When children complete two consecutive visits at a level equal to or safer than the average adult performance, they will be considered "competent" pedestrians functioning like an adult and training will be discontinued. Adult performance will be defined based on previous research with >300 adults.

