## 5.2 MEASURES TO MINIMIZE BIAS: RANDOMIZATION

Random assignment to the condition in which the child received training will be conducted using simple randomization by asking children to draw a slip of paper from a large envelope at the end of baseline data collection.

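### The primary ANCOVA may adjust for attention during training, a post-randomisation variable that the platform can change, and so remove part of the effect being tested

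*Combined protocol and SAP*

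**What the plan says.** Section 8.3 names covariates that may influence the outcomes, "including age, gender, temperament, attention during intervention, pedestrian experience, and verbal intelligence". It treats them all alike: "Because children will be randomized to the interventions, we expect these covariates to be balanced across intervention groups". Each is to be tested against arm, and then: "If differences emerge, those variables will be included as covariates in primary analyses". No criterion for a difference is given. No exception is made for variables observed after randomisation, and no analysis without them is named as primary.

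The rule applies to the Aim 1 ANCOVA of change in start delay. It carries over to Aim 3 (start delay and unsafe crossings), where "we will test the aim with the same hypothesis, analyses, and assumptions as in Specific Aim 1".

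Two other sections fix the timing and the contrast. Section 5.2 randomises children by having them "draw a slip of paper from a large envelope at the end of baseline data collection". The Training Protocol in Section 5.1.1 says that sessions "will be identical in both groups except for the VR platform used".

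**The concern.** Age, gender, temperament and verbal intelligence are characteristics a child brings to the trial. Pedestrian experience is too, if taken at baseline. Attention during the intervention is not. It does not exist until training starts, and training starts after allocation, so randomisation gives no reason to expect balance on it. Since platform is the only planned difference between the arms, a systematic difference in attention would itself be an effect of platform.

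Chance imbalance aside, the rule therefore adjusts for attention mainly when the platform has changed it. Aims 1 and 3 ask whether smartphone training as delivered is not inferior to kiosk training. That is a total effect, not an effect at equal attention. If children attend less on the smartphone, adjustment hides part of a real deficit and favours a false non-inferiority claim. If they attend more, it hides a real advantage and costs power.

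**Working it through.** **Inputs from the documents (Section 8.2).** Aim 1 start delay: 216 per group, SD 0.50, margin 0.12, power 80%, type I error 0.05. Aim 3 unsafe crossings: 216 per group, SD 0.18, margin 0.05, alpha 0.025, power 82%.

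**Reproducing the plan's figures.**
- Aim 1: n = 2 × SD² × (z₁₋α + z₁₋β)² / margin². With one-sided 0.05 this is 2 × 0.25 × (1.645 + 0.842)² / 0.0144 ≈ 215 per group, against 216 stated. One-sided 0.025 gives 273. The document does not state sidedness, so one-sided 0.05 is inferred from this match.
- Aim 3: SE = 0.18 × √(2/216) = 0.0173, and power = Φ(0.05/0.0173 − 1.960) ≈ 82%, as stated.

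**Assumptions not in the documents.** These are d, r and a two-sided 0.05 level for the imbalance test. The stated SD is taken as the residual SD after baseline adjustment. A positive smartphone-minus-kiosk difference in change means the smartphone is worse; this is the direction the text intends, since the labels in the printed hypothesis are not defined.

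**How often attention is selected.** The imbalance statistic is centred at d / √(2/216) = d / 0.0962. At d = 0.3 this is 3.12, so selection has probability Φ(3.12 − 1.96) ≈ 88%. The same step gives about 18% at d = 0.1, 55% at d = 0.2 and over 99% at d = 0.5.

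**Shift once attention is in the model: r × SD × d.** At d = r = 0.3:
- Start delay: 0.3 × 0.50 × 0.3 = 0.045 s, which is 38% of the 0.12 margin.
- Unsafe crossings: 0.3 × 0.18 × 0.3 = 0.016, which is 32% of the 0.05 margin.

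**Hand check at d = r = 0.3, attention always adjusted, true deficit 0.12.** SE = 0.50 × √(1 − 0.09) × 0.0962 × √(1 + 0.09/4) ≈ 0.0464. False non-inferiority = Φ(0.045/0.0464 − 1.645) ≈ 25%. The plan's rule should give slightly less, because it selects attention in 88% of trials.

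**Simulation of the plan's rule.** 216 per group; 60,000 trials per scenario for the Aim 1 false-claim column and 20,000 or more elsewhere. Ranges are for r = 0.1 to 0.3. False-claim columns set the true deficit at the margin with attention lower on the smartphone. The power column sets no true difference with attention higher on the smartphone.

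| d | Aim 1 false non-inferiority | Aim 1 power | Aim 3 unsafe crossings, false non-inferiority |
|---|---|---|---|
| 0 | about 5% | 80% | 2.5% |
| 0.1 | 5.4–6.3% | 77–79% | about 3% |
| 0.2 | 6.7–12.2% | 66–76% | 3.5–7% |
| 0.3 | 8.7–23.0% | 50–71% | 5–15% |

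At d = 0.5 the Aim 1 false-claim rate is 12.7–47.3%. Aim 3 power at d = r = 0.3 falls from 82% to 54%. With a true Aim 1 deficit of 0.12, the mean estimate under the rule is about 0.097 at d = 0.2, r = 0.3 and about 0.077 at d = r = 0.3. Leaving attention out keeps the Aim 1 false-claim rate at about 5% throughout.

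**The case against.** The strongest reply is that the harm is not demonstrated. The measure appears only in the Section 8.3 list. It has no instrument, rater or scale, it is absent from the covariates in Section 7.1, and nothing equates it with the secondary outcome of attention to traffic. Section 5.1.1 says the two systems share their virtual environment, game logic and data capture, and that most users do not notice the kiosk's change of viewpoint. The smartphone's contrasting feature, "In the smartphone VR, the virtual world remains at first-person view, as the viewpoint follows the avatar across the street", concerns what happens after the child has decided to cross. At d = 0.1 the Aim 1 error rises by only about a point, and at d = 0 not at all.

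This stands as a limit on size. That the platform can move attention is an inference, resting more on headset against three screens and button against pressure plate than on viewpoint. It does not rescue the rule. The name places the measure after randomisation, and a pre-specified primary analysis should be valid whether or not the platforms differ on it.

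A second point also stands. If an unmeasured factor drives both attention and improvement, r is partly non-causal. Adjustment then does not cleanly remove a mediated effect and can add bias of another kind. The shift away from the total effect is still r × SD × d, so the case for leaving attention out is unchanged.

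Adjusting for the baseline outcome, which the ANCOVA already does, does not prevent any of this.

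**Conclusion.** The concern holds. As written, the rule can put a post-randomisation variable into the primary model for Aims 1 and 3, and it does so most reliably when the platform has affected that variable. The comparison then no longer estimates the total platform effect, and the error can favour or oppose non-inferiority.

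The size is conditional on d and r, which the documents do not give: negligible when d is near zero, and at d = r = 0.3 large enough to raise Aim 1 false claims from 5% to about 23% or cut power from 80% to 50%. These figures also rest on the assumed 0.05 imbalance test and the inferred one-sided 0.05. The defect in the rule depends on none of them. It should be corrected because it governs the primary tests and correction is nearly free.

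**What to change.** Delete attention during intervention from the covariates eligible for the primary models of Aims 1 and 3, and state that only variables measured before the randomisation draw may enter. Report attention by arm descriptively, or in a separately labelled mediation analysis, with the measure defined. This is an edit to one list. It needs no new data and leaves the sample size at 216 per group.

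A separate, optional improvement is to replace the imbalance test with a fixed set of prognostic baseline covariates alongside the baseline outcome. This is for efficiency and pre-specification only; selecting true baseline covariates by imbalance does not bias the estimate. In simulation with five independent covariates, power was 81% under the plan's rule against 87% with fixed adjustment if each correlates 0.2 with outcome, but 80% against 81% at 0.1 (both correlations assumed). The cost is a few degrees of freedom out of about 430, a rule for missing covariate values so that no child is dropped, and a check that each covariate is measured before randomisation, since Section 7.1 does not give the timing.

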## 7 STUDY ASSESSMENTS AND PROCEDURES

### 7.1 STUDY ASSESSMENTS

In all pedestrian simulations (both virtual and streetside), several measures will be collected. Unsafe crossings will be the primary outcome, defined as the sum of “hits” with simulated vehicles, plus “close call” instances when the child was within one second of being hit by an oncoming vehicle. We also will assess several secondary measures, including start delay (temporal lapse between a safe gap between vehicles emerging and children entering that gap to cross the street), time to contact (shortest distance between children and an oncoming virtual vehicle), attention to traffic (looks left and right divided by wait time), missed opportunities (rejected gaps  $\geq$  1.5 times participant’s crossing time), wait time (average time waiting to cross, divided by cars that pass while waiting), and gap size (temporal gap crossed within).

We will collect other measures as potential covariates. Parents will report basic demographic data (e.g., child gender, race/ethnicity, birthdate; family SES), child temperament, and children’s pedestrian behavior and habits. Children will complete a screener of verbal intelligence.

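### Beyond the outcome's baseline value, covariates enter the primary ANCOVA only if an unspecified balance check shows a group difference, so the model is not fixed in advance and available precision goes unused

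*Combined protocol and SAP*

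**What the plan says.** Section 8.3 names six variables, "including age, gender, temperament, attention during intervention, pedestrian experience, and verbal intelligence", and gives the reason for attending to them: "Several covariates may impact the relation between the intervention and the outcome measures of interest". It expects randomisation to balance them, and then sets a check: "To test this, we will assess the relation between each covariate and intervention group". The consequence is: "If differences emerge, those variables will be included as covariates in primary analyses". No test, significance level or size of difference is given. No other section fixes an adjusted model; section 7.1 says only "We will collect other measures as potential covariates".

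One term is unconditional. The ANCOVA asks whether the between-group difference in change "falls below the non-inferiority margin, after adjustment for the baseline measure". The balance rule therefore governs only the covariates added to that term.

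The Specific Aim 3 paragraph of 8.3 carries the Aim 1 analyses over to two primary outcomes, start delay and unsafe crossings, each at post-intervention and at the 6-month follow-up. Allocation, in section 5.2, is by "simple randomization by asking children to draw a slip of paper from a large envelope at the end of baseline data collection".

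**The concern.** A covariate is worth adjusting for because it predicts the outcome. The rule selects on a different property, its relation to randomised group. Under simple randomisation that relation is chance for anything measured before the draw. A predictive covariate that happens to be balanced stays out, and one that predicts nothing but happens to differ goes in.

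Two things are at stake:

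- **Pre-specification.** With five baseline candidates there are 2^5 = 32 possible primary models. Which one applies is settled only after group data have been examined, against a threshold that nobody has written down.
- **Precision.** The covariates are to be collected anyway, and the rule uses them in only a minority of trials.

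The list also contains attention during intervention. Children are randomised before training starts, so this is measured after randomisation and the VR platform could affect it. The rule could put it into the primary model.

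**Working it through.** **Inputs.** Section 8.2 gives, for Aim 1, margin 0.12, SD 0.50, 216 per group, "with 80% power and type I error rate of 0.05" (sidedness not stated); and for Aim 3 unsafe crossings, margin 0.05, SD 0.18, alpha 0.025, power 82%. A true difference of 0 is implied. Two inputs are assumptions: that SD 0.50 is the SD after adjustment for the baseline outcome, and R2, the share of that remaining variance explained by the additional covariates. The documents give no R2, so a range from zero is shown.

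**1. The plan's own figures.** n per group = 2 × (1.645 + 0.842)^2 × 0.50^2 / 0.12^2 = 214.7, so 215 by the normal formula. The t-based calculation gives 216 with power 80.1%. The stated 216 therefore reproduces with a one-sided 0.05; a one-sided 0.025 would need 273. For Aim 3, 0.05 / (0.18 × √(2/216)) − 1.96 = 0.927, which is 82.3% power against 82% stated.

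**2. How often the rule changes the model.** Assuming five independent covariates each tested at 5%, P(at least one flagged) = 1 − 0.95^5 = 22.6%. At a 10% threshold it is 1 − 0.90^5 = 41.0%.

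**3. Power with fixed adjustment.** Power = Φ(margin / (SD × √(1 − R2) × √(2/216)) − z). For Aim 1 at R2 = 0.10, the SD becomes 0.50 × √0.90 = 0.474, the standard error 0.0456, and power Φ(2.629 − 1.645) = 83.8%.

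| Assumed R2 | Aim 1 power | n per group for 80% | Aim 3 unsafe crossings, power |
|---|---|---|---|
| 0 | 80.2% | 215 | 82.3% |
| 0.05 | 82.0% | 204 | 84.2% |
| 0.10 | 83.8% | 194 | 86.1% |
| 0.20 | 87.4% | 172 | 89.8% |

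**4. Power under the plan's rule.** This was simulated: 216 per group, residual SD 0.50, five independent normal covariates with equal effects, balance t-tests at 5%, one-sided 5% non-inferiority test, baseline outcome always in the model. There were 8,000 trials per scenario (Monte Carlo error √(0.8 × 0.2 / 8000), about 0.4 points). The 5% row is from a separate run of 5,000 trials.

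| Assumed R2 | Baseline only | Plan's rule | Fixed adjustment |
|---|---|---|---|
| 0 | 80.4% | 80.2% | 79.7% |
| 0.05 | 80.6% | 80.6% | 82.0% |
| 0.10 | 80.9% | 81.1% | 83.5% |
| 0.20 | 80.1% | 81.0% | 86.5% |

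The reason is simple. At a 5% threshold each covariate enters in about 5% of trials, so with R2 = 0.10 the rule removes on average about 0.05 × 10% = 0.5% of the residual variance. At R2 = 0.20 the mean standard error is 0.0481 with baseline only, 0.0480 under the rule and 0.0433 with fixed adjustment.

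**5. Type I error.** With the true difference set at the margin, the rule rejected in 4.8, 5.1 and 4.9% of trials at R2 = 0, 0.10 and 0.20, against a nominal 5%.

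**The case against.** The strongest case against is that little is at risk. Section 8.2 sizes the trial on a two-sample comparison of means and takes no credit for covariates, so planned power survives under the rule. The baseline outcome, often the most useful covariate, is already in the model. The check looks at covariates and group, not at outcomes, and does not inflate type I error at a fixed threshold. All of this stands.

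The size of the gain is also uncertain. R2 may be zero. Section 8.3 says only that the covariates may matter, and section 4.1 limits age to 7 or 8 years, so a reader who takes them to be strongly prognostic goes beyond the text. Section 8.2 does not say whether SD 0.50 is before or after baseline adjustment. If it is before, power already exceeds 80%. With an assumed correlation of 0.4, the SD falls to 0.50 × √(1 − 0.16) = 0.458 and power is about 86%; a further 10% explained variance then adds about 3 points.

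It can also be said that stating a threshold would close the discretion. It would, but the rule would still select on chance imbalance. Finally, forcing covariates into a complete-case model could drop children and offset the gain. That is a fair warning, and the fix has to deal with it.

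**Conclusion.** The point holds as a worthwhile improvement. The rule selects covariates on the wrong criterion, leaves the primary models for Aims 1 and 3 open until group data are seen, and recovers almost none of the precision the covariates could give. For assumed R2 of 0, 5, 10 and 20%, and SD 0.50 read as the SD after baseline adjustment, Aim 1 power is about 80, 82, 84 and 87% with fixed adjustment, against about 80 to 81% under the rule. With five independent covariates tested at 5%, both assumptions, the rule would alter the model in 23% of trials.

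Three stronger readings are tempting, and the documents do not support them:

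- **The trial is underpowered, or 216 is wrong, because of this rule.** The sample size reproduces without any covariates, and the rule does not lower power below plan.
- **The rule inflates type I error.** At a fixed 5% threshold it does not. The unstated threshold leaves room for choice, but nothing in the documents shows that it would be used selectively.
- **The plan makes all baseline adjustment conditional.** The outcome's baseline value is always included.

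**What to change.** In section 8.3, delete the balance-test selection rule and state instead:

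- The primary ANCOVA for each outcome, in Aims 1 and 3, always includes its baseline value plus age, gender, verbal-intelligence score, a named temperament score or scores, and parent-reported pedestrian experience, whatever their balance.
- These covariates are measured before the randomisation draw. Section 7.1 does not say when parents report them, so the timing should be written down and the exact scores named.
- Attention during intervention is not in the primary model.
- Missing baseline covariate values are imputed by a simple method that ignores treatment group, such as the overall mean, so that no child is dropped.
- The ANCOVA with the baseline outcome only is reported as a sensitivity analysis, and balance is described without p-values.

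The change is a few sentences, made before group data are examined. The variables are already to be collected. The cost is about five degrees of freedom out of about 430, somewhat more if several temperament scales are named. If the covariates predict nothing there is no gain, and the price is negligible: the simulated standard error rises from 0.0481 to 0.0484.
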